6.3. Measures to Minimize Bias: Randomization and Blinding

This is an open-label, nonrandomized study. In order to minimize bias, subjects will be assigned sequentially as they are enrolled into the study using the inclusion and exclusion criteria outlined in [Section 5.1](#) and [Section 5.2](#), respectively. Enrollment will be confirmed by the Sponsor Medical Monitor after review of all supporting documentation for eligibility criteria. Subjects

will be assigned a screening number at the time of signing the ICF. If a subject is a screen failure, the number will not be reassigned.

For Italy only, the eligibility form will not be used to allow the Sponsor or contract research organization (CRO) to make any medical decisions for the subject. Instead, it will be used for Sponsor and CRO to confirm that the subject's eligibility check has been fully completed (eg, no inclusion/exclusion criteria are missing, and all of the screening procedures have been completed), with the intention to ensure subject safety and data integrity.

6.4. Study Treatment Compliance

6.4.1. Compliance Instructions

Dosing instructions will be provided to the subject, and subject compliance with study treatment will be reviewed at each visit. Compliance will be assessed by counting returned RMC-4630 capsules, in conjunction with subject diary information and subject questioning. Subject compliance for sotorasib administration will only be assessed by reviewing subjects' diaries and questions asked during clinic visits. The investigator should follow the guidance provided in [Section 8.5](#) if a subject is suspected to have taken greater than the assigned dosage.

6.4.2. Missed Dose

RMC-4630: If a subject misses a Day 1 (D1) dose of RMC-4630, it should be taken as soon as the missed dose is discovered. The D2 dose should then follow 24-hours after. If the subject misses D2 dose, it should be taken as soon as the missed dose is discovered, provided there is at least a 24-hour gap between D1 dose and D2 dose. If the gap between D1 and D2 dose is more than 48 hours, the D2 dose should not be administered and should be recorded as an omission. The subject should not administer more than the recommended dose.

Sotorasib: If a dose of sotorasib is missed, or if vomiting occurs when the dose is taken, the subject should resume dosing with the next scheduled dose.

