4.3. Dose Justification

4.3.1. RMC-4630

RMC-4630 is being studied in the clinic as a monotherapy in Study RMC-4630-01 (NCT03634982), and in various other combination studies. RMC-4630 has been tested at various dose levels and schedules including daily dosing, intermittent dosing schedule on [REDACTED] and [REDACTED]. As of 16 November 2020, [REDACTED] have been treated with RMC-4630

monotherapy; the RP2DS was determined to be [REDACTED] of each week in a 21-day cycle. At this dose level, the plasma concentrations of RMC-4630 were above those predicted to be clinically active, based on preclinical models. The C_{max} reached, and often exceeded, the apoptotic threshold (75% effective concentration [EC₇₅]), defined as plasma concentrations that were associated with induction of tumor regressions or cell death in preclinical models. Trough concentrations at the end of each week were close to the 50% effective concentration (EC₅₀) for RAS signaling pathway inhibition in tumors, which was predicted to be sufficient to permit normal tissue recovery and therefore contribute to tolerability.

Furthermore, RMC-4630 and sotorasib combination is being tested in an ongoing Amgen-sponsored Phase 1b platform (CodeBreaK 101C). CodeBreaK 101C was initiated in May

2020 and is currently dosing subjects at RMC-4630 [REDACTED]

[REDACTED] of each week in a 21-day cycle and [REDACTED] of each week in a 21-day cycle). This Phase 2 study (RMC-4630-03) will have a safety run-in period in which RMC-4630 will be administered at [REDACTED] of each week in a 21-day cycle as the starting dose with the option of escalating to RMC-4630 [REDACTED] of each week in a 21-day cycle if tolerated per modified toxicity probability interval 2 (m-TPI2).

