6. STUDY TREATMENT

6.1. Study Treatments Administered: RMC-4630 and Sotorasib

The study treatment for this protocol is combination therapy of the investigational drug product RMC-4630 and the marketed product sotorasib.

RMC-4630 [REDACTED] will be administered PO on [REDACTED] of each week in a 21-day cycle (ie, Days 1, 2, 8, 9, 15, and 16 of each 21-day cycle). RMC-4630 capsules should not be crushed or chewed.

Sotorasib [REDACTED] mg will be administered PO QD per instructions provided in the current Sotorasib IB. At the Sponsor's discretion, new subjects enrolling on this trial may be treated at sotorasib 240 mg in combination with RMC-4630 (see [Table 4](#)). Subjects currently enrolled at sotorasib 960 mg may continue at their current dose or dose reduce based on discussion with the Sponsor Medical Monitor. Subjects developing toxicities at sotorasib [REDACTED] may dose reduce to sotorasib [REDACTED] or discontinue treatment.

For the main protocol, the subject should administer the study treatment at approximately the same time every day except for clinic visit days as listed in the SoA ([Table 1](#)). On these clinic visits, the subject should await instruction from the study staff to coordinate with the timing of PK and/or biomarker sampling.

Subjects deriving benefit from treatment who enter the Extended-Use phase of the study should continue treatment without interruption.

Table 4: Study Treatment Administered: RMC-4630 and Sotorasib

Component Name	Drug Product Information
Treatment Name	RMC-4630 and sotorasib combination therapy
Type	Drugs
Dose Formulation	RMC-4630: PIC drug product Sotorasib: tablet
Unit Dose Strengths	RMC-4630: [REDACTED] g Sotorasib: 120 mg
Dosage Levels	RMC-4630: [REDACTED] for a treatment cycle of 21 days Sotorasib: [REDACTED] QD
Route of Administration	PO with water after 1 hour fast; no food or drink (other than water) allowed for 1 hour after administration for RMC-4630 alone or RMC-4630 in combination with sotorasib. PO; no restrictions on food for sotorasib when taken alone.
Investigational Product	RMC-4630 in combination with Sotorasib IMP to be supplied for all sites unlabeled drug product sourced from Amgen

Table 4: Study Treatment Administered: RMC-4630 and Sotorasib (Continued)

Component Name	Drug Product Information
Sourcing	RMC-4630: Manufactured and provided centrally by the Sponsor through the third party CMO Sotorasib: IMP (unlabeled drug product supplied by Amgen) to be provided by Sponsor

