8.5. Treatment of Overdose

For this study, any dose of RMC-4630 or sotorasib that is greater than the intended dose per administration or 2 administrations at the intended dose or more of sotorasib within <12 hours (QD dosing) or 2 administrations of RMC-4630 <12 hours apart (BIW D1, D2 dosing) will be considered an overdose. There is no clinical experience with an overdose of RMC-4630 in human clinical trials. No experiments have been performed to determine whether the effects of an overdose can be reversed, and there are no known antidotes.

Revolution Medicines does not recommend specific treatment for an overdose. The individual should be monitored clinically, and supportive care should be undertaken as clinically indicated.

In the event of an overdose, the investigator should:

1. Halt the dispensation and administration of the involved medication. The investigator may also hold the second medication based on his/her clinical judgement.
2. Contact the Medical Monitor immediately.
3. Closely monitor the subject for any AE/SAE, ECG, and laboratory abnormalities (blood glucose, liver function tests, creatinine, blood urea nitrogen (BUN), creatine phosphokinase (CPK), and complete blood count) until RMC-4630 and/or sotorasib can no longer be detected systemically.
4. Obtain a plasma sample for PK analysis within 1 to 2 days from the date of the last dose of study intervention if requested by the Medical Monitor (determined on a case-by-case basis). Note, the PK sample collection applies to the main protocol only and not the Extended-Use phase.
5. Document the quantity as well as the duration of the overdose in the eCRF.
6. Decisions regarding resumption of study treatment will be made by the investigator in consultation with the Sponsor's Medical Monitor based on clinical evaluation of the subject.

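### Section 6.4.2 sets no limit on how late a missed weekly D1 dose of RMC-4630 may be taken, so following it between visits can produce four consecutive daily doses

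*Protocol*

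**What the plan says.** Protocol Section 6.1 schedules RMC-4630 on "Days 1, 2, 8, 9, 15, and 16 of each 21-day cycle": two consecutive days each week, then five days off.

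Section 4.3.1 gives the reasoning for the off-days. Trough concentrations at the end of each week were close to the EC50 for pathway inhibition, "which was predicted to be sufficient to permit normal tissue recovery and therefore contribute to tolerability".

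Section 6.4.2 treats the two weekly doses differently when one is missed:

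- **Late D1:** "If a subject misses a Day 1 (D1) dose of RMC-4630, it should be taken as soon as the missed dose is discovered". Then: "The D2 dose should then follow 24-hours after". No latest time is given.
- **Late D2:** "If the gap between D1 and D2 dose is more than 48 hours, the D2 dose should not be administered", and the dose is recorded as an omission.
- **General restraint:** "The subject should not administer more than the recommended dose". No period is attached to this.

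Section 8.5 defines an RMC-4630 overdose in two ways. One is an administration larger than intended. The other is by interval: "2 administrations of RMC-4630 <12 hours apart (BIW D1, D2 dosing) will be considered an overdose".

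**The concern.** The schedule and its justification depend on the dose-free days between one weekly pair and the next. The missed-dose rule limits lateness for the second dose of a pair but not for the first. Because D2 is tied to the late D1, the whole pair can move towards the next scheduled pair, which itself stays where it was.

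The result can be a run of daily dosing reached by complying with the protocol, not by departing from it. If the overdose definition does not recognise the pattern, the steps that follow an overdose in 8.5 (contact with the Medical Monitor, ECG and laboratory monitoring) do not start. At stake is the consistency of a dosing instruction with the tolerability argument on which the schedule rests.

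**Working it through.** The plan states no figure to reproduce, so the check applies the written rule to the calendar.

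**Inputs.** Planned days 1, 2, 8, 9, 15, 16 (6.1). Late D1 taken on discovery, D2 24 hours later, D2 omitted only if the D1-D2 gap exceeds 48 hours (6.4.2). Overdose if an administration exceeds the intended dose or two fall less than 12 hours apart (8.5). RMC-4630 levels of 140 mg and 200 mg (SAP 2.2.1).

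**Planned pattern.** From Day 9 to Day 15 is 6 × 24 = 144 hours. There are at most two consecutive daily doses, and at most two doses in any seven days.

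**Which doses are exposed.** Table 1 places Cycle 1 visits on Days 1, 8 and 15. Its footnote 30 has RMC-4630 given in clinic on Cycle 1 visit days and on Day 1 of later cycles. Section 1.3 reduces visits to Day 1 of each cycle beyond Cycle 2. The weekly D1 doses with no visit are therefore mainly Day 8 and Day 15 from Cycle 3 onward. Day 8 of Cycle 2 also has none, but that cycle has a Day 15 visit.

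**Day 8 missed and found on day d.** Make-up doses fall on days d and d+1.

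- Gap before the late pair, from Day 2: 24 × (d − 2) hours.
- Gap from make-up D2 to the scheduled Day 15 dose: 24 × (15 − (d + 1)) = 24 × (14 − d) hours.

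| Found on Day | Doses from then to Day 16 | Gap before late pair (h) | Gap to next pair (h) | Most doses in any 7 days |
|---|---|---|---|---|
| 9 | 9, 10, 15, 16 | 168 | 120 | 3 |
| 10 | 10, 11, 15, 16 | 192 | 96 | 4 |
| 11 | 11, 12, 15, 16 | 216 | 72 | 4 |
| 12 | 12, 13, 15, 16 | 240 | 48 | 4 |
| 13 | 13, 14, 15, 16 | 264 | 24 | 4 |
| 14 | 14, then make-up D2 and scheduled D1 both on 15, then 16 | 288 | 0 (collision) | not defined by the rule |

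**Checks on the Day 13 case.**

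- The D1-D2 gap is 24 hours, within the 48-hour limit.
- The shortest gap is 24 hours, so the 12-hour overdose test is not met.
- Each administration is at the assigned dose, so the amount test is not met.
- Days 8 to 14 contain two doses and Days 15 to 21 contain two, so the weekly count is as assigned.
- Over the four days the sum is 4 × 140 = 560 mg or 4 × 200 = 800 mg, against a planned maximum of 280 mg or 400 mg in any four days.
- The cycle total is unchanged at six doses: 840 mg or 1,200 mg.

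**Day 15 missed and found on Day 20.** Doses fall on Days 20 and 21 and on Days 1 and 2 of the next cycle, again 24 hours between pairs. The third of these is given in clinic.

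**Alternative reading.** If the 48 hours ran from the scheduled D1 time, discovery on Day 13 would give Days 13, 15 and 16, with no run of four. Discovery on Day 14 would still give Days 14, 15 and 16. The text measures the gap between the D1 and D2 doses, so this is not its natural meaning, and even so D1 itself has no limit.

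**The case against.** The strongest reply is that the pattern is rare and largely supervised. That stands for much of the calendar. All weekly D1 doses in Cycle 1, and Day 1 of every later cycle, are given in clinic, and 7.3 requires the site to reschedule a missed visit as soon as possible. When a Day 15 dose is made up on Day 20, the next-cycle Day 1 visit comes before the third consecutive dose, and 6.4.1 requires a compliance review there. The full four-day run without a visit needs a Day 8 dose found missed exactly on Day 13. The documents do not say how often that would happen.

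It is also fair that time off drug is moved, not simply lost: 264 hours precede the late pair and the cycle total does not rise. Section 4.3.1 mentions that daily dosing was itself tested, with the levels redacted, so no quantified hazard can be drawn from the documents. One may add that 6.4.2 is silent on the point and does not openly contradict 4.3.1. But following it yields dosing days that 6.1 does not contain and an interval that 4.3.1 does not contemplate.

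Other safeguards help less than they seem to. Section 6.7 requires missed doses to be recorded on the eCRF, but a record sets no limit. Section 6.4.1 refers sites to 8.5 only when more than the assigned dosage is suspected. The general restraint in 6.4.2 does count against doubling up in the Day 14 collision, but it has no weekly or rolling definition that would reach the Day 13 case.

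A reader might infer two further harms, and neither is supported:

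- **Distorted DLT evaluation.** The DLT window is Cycle 1, where each weekly D1 dose falls on an in-clinic dosing day, and SAP 6.1 defines Day 1 as the first-dose date.
- **Distorted pre-dose trough.** The sampling day in Table 2 is redacted, 8.6 records actual sampling times, and 6.7 documents missed doses.

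**Conclusion.** The gap is real and bounded. A late D1 dose has no limit, and the handling of the next pair is unstated. In weeks without a visit, compliance with 6.4.2 can cut the planned 144 hours before the next pair to 24 and give four consecutive daily doses that 8.5 does not recognise as an overdose. Earlier discovery leaves 48 to 120 hours; discovery one day later produces a collision that the rule does not resolve.

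This does not show excess dosing over a cycle, a measured toxicity risk, or any effect on the escalation decision or the PK summaries.

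The conclusion assumes that the next pair stays on its scheduled days and that the 48 hours is measured between the doses actually taken. The pharmacy manual and the subjects' dosing instructions are not among the documents and may say more. The point merits correction despite its narrow reach, because the pattern comes from following a written dosing instruction.

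**What to change.** The sponsor should reconcile Section 6.4.2 with 4.3.1, 6.1 and 8.5 so that three things agree with the intermittent schedule: the instruction for a missed weekly D1 dose, the handling of the next scheduled pair when the make-up pair falls close to it or on it, and the reporting of a shortened off-period. The clinical rule and any value in it are for the sponsor to set.

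The cost is a few sentences and an update to the dosing diary. Depending on the rule chosen, some doses found late may become recorded omissions.

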6.5. Permitted Concomitant Therapy

Supportive care (eg, antiemetics, analgesics, blood transfusions, hematopoietic growth factor support) may be used at the investigator's discretion and in accordance with institutional procedures. Localized radiotherapy used for palliative purposes may be considered after discussion with the Medical Monitor. Anticoagulation with low-dose aspirin, low-molecular weight heparin (LMWH), and direct Factor-Xa inhibitors are allowed. Contraceptives are also allowed throughout the study (see [Section 5.1](#)).

If an acid reducing agent cannot be avoided, administer sotorasib and RMC-4630 either 4 hours before or 10 hours after a local antacid.

Avoid coadministration with CYP3A4 substrates for which minimal concentration changes may lead to therapeutic failures of the substrate. If coadministration cannot be avoided, adjust the substrate dosage in accordance with the current Sotorasib IB.

Avoid coadministration with P-gp substrates for which minimal concentration changes may lead to serious toxicities. If coadministration cannot be avoided, decrease the substrate dosage in accordance with the current Sotorasib IB.

A local antacid (eg, calcium carbonate, sodium bicarbonate, or bismuth subsalicylate-containing agents such as Tums, Alka-Seltzer, Pepto-Bismol, etc.) may be permitted after discussion with the Sponsor Medical Monitor if RMC-4630 is administered either 4 hours before or 10 hours after the local antacid.

Any medication or vaccine, including over-the-counter or prescription medicines, vitamins, and/or herbal supplements, that the subject is receiving at the time of enrollment or receives during the study, must be recorded along with the following:

- Reason for use
- Dates of administration, including start and end dates
- Dosage information, including dose and frequency
- Route of administration

The Medical Monitor should be contacted if there are any questions regarding concomitant or prior therapy.

6.6. Prohibited Concomitant Therapy

In addition to prohibited medications/foods listed in the Exclusion Criteria ([Section 5.2](#)), a complete list of prohibited medications during study treatment is provided in [Appendix 8](#).

The following medications are prohibited while on study treatment:

- PPIs and H2-blockers
- Medications known to prolong QTc interval
- Anti-cancer therapy (except study treatment medications)
- Strong CYP3A4 inhibitors and inducers
- Strong P-gp inhibitors
- Known CYP3A4 and P-gp sensitive substrates (with a narrow therapeutic index), that were not reviewed and approved by the principal investigator

6.7. Dose Modification

A 21-day cycle will be maintained, and dose interruption will be noted in the 21-day cycle schedule. Two types of dose modifications are allowed: dose interruption and dose level reduction. Any allowed dose modification and any deviation from the intended dose (missed doses or overdoses due to subject error) should be documented on the dose electronic Case Report Form (eCRF).

In general, dose adjustments should be based on attribution to a particular treatment. Certain AEs are known to be associated with administration of sotorasib (see current Sotorasib IB), whereas others have been observed with the administration of RMC-4630 in clinical or preclinical studies (see current RMC-4630 IB). However, because both components of the study treatment affect the RAS signaling pathway, overlapping toxicities are likely to be observed.

If RMC-4630 is discontinued due to toxicity, sotorasib monotherapy can be continued as it is the standard-of-care in this patient population. However, if sotorasib is discontinued due to toxicity

reasons, RMC-4630 continuation as monotherapy may be considered, provided that the subject per investigator discretion is clinically benefitting from treatment with no evidence of disease progression (and approval by the Sponsor's Medical Monitor).

Depending on the RMC-4630 starting-dose level, up to 2 dose-level reductions for [REDACTED] and one dose-level reduction for the [REDACTED] are permitted for upon discussion with the Sponsor Medical Monitor. Depending on the sotorasib starting-dose level, up to 2 dose-level reductions for 960 mg and one dose-level reduction for 240 mg are permitted upon discussion with the Sponsor's Medical Monitor. Guidance for dose reduction for both components of the study treatment is presented in [Table 5](#). If more than 2 dose reductions are required for either RMC-4630 or sotorasib 960 mg, or more than one dose reduction is required for sotorasib 240 mg, administration must be discontinued for that component and treatment with the remaining single component (RMC-4630 or sotorasib) may be considered, depending on investigator assessment of clinical benefit and discussion with the Sponsor's Medical Monitor. Dose modification guidelines for a subset of common AEs seen with RMC-4630 and/or sotorasib (per the current Sotorasib IB) are shown in [Table 6](#). General guidance for dose modification is presented in [Table 7](#). The investigator or treating physician should use his/her best medical judgement for management.

When reducing dose, the dose of one or both agents (RMC-4630 and sotorasib) could be reduced depending on which may be causing the toxicity.

Table 5: Dose Reduction Guidelines with RMC-4630 and Sotorasib

Dose Level	Treatment and Dosage		Sotorasib (QD)
	RMC-4630 ([REDACTED] in a 21-Day Cycle)		
1 (subject starting dose level) ¹	[REDACTED]	960 mg	240 mg
-1 (dose reduction from starting dose for either component of study treatment if needed)	[REDACTED]	480 mg	120 mg
-2 (dose reduction from starting dose for either component of study treatment if needed)	[REDACTED]	240 mg	NA

Abbreviations: [REDACTED]; NA = not applicable; QD = once daily.

¹ Starting dose level represents the subject's assigned dose level at enrollment. For example, if the subject enrolled at the RMC-4630 140 mg dose level (default starting dose), they would dose reduce to 100 mg. A subject enrolled at the RMC-4630 200 mg dose level would dose reduce to 140 mg, followed by reduction to 100 mg as necessary.

Table 6: Dose Modification Guidelines for RMC-4630 and Sotorasib

AE	Action
Thrombocytopenia	
Thrombocytopenia associated with clinically significant bleeding, at any level: Hold RMC-4630 and sotorasib and follow hemorrhage recommendations.
 
Uncomplicated thrombocytopenia (without clinically significant bleeding):
 
Grade 1-2: Continue treatment at current dose level for both components of study treatment and monitor closely.
 
Grade 3-4: Manage per institutional guidelines and interrupt RMC-4630 dosing until the event recovers to Grade 1 or within normal limits or returns to baseline. If recovery occurs, resume RMC-4630 at one dose level lower. If Grade 3-4 events recur, hold dose until recovery to Grade 1 or within normal limits or returns to baseline and a second dose reduction may be considered. If the subject continues to experience high-grade thrombocytopenia, RMC-4630 may be discontinued permanently and sotorasib monotherapy can be continued.
 
Subjects on anticoagulant(s)
 
Subjects receiving anticoagulant therapy should be monitored closely for evidence of treatment-emergent thrombocytopenia. Subjects who develop treatment-emergent thrombocytopenia may need to be managed more conservatively, due to increased risk of bleeding.

Neutropenia/ Febrile Neutropenia/ Anemia/ Pancytopenia	
Assess for other causes. Hold concomitant medications associated with myelosuppression.
 
Grade 3 neutropenia: Hold RMC-4630 if clinically indicated until the event recovers to Grade 1 or within normal limits or returns to baseline. If improvement occurs within 3 weeks, restart RMC-4630 at one dose level lower. If there is no improvement within 3 weeks, or upon recurrence of Grade 3 neutropenia, additional dose reduction of RMC-4630 or permanent discontinuation of RMC-4630 can be considered.
 
Grade 3 febrile neutropenia: Hold RMC-4630 and sotorasib until fever resolves and ANC recovers to Grade 1 or is within normal limits or returns to baseline. If improvement occurs within 2 weeks, restart RMC-4630 one dose level lower. If there is no improvement within 2 weeks, discontinue RMC-4630 and sotorasib.
 
Grade 3 anemia: Assess transfusion history. Transfuse per institutional guidelines. Hold RMC-4630 if clinically indicated until the event recovers to Grade 1 or within normal limits or returns to baseline. If improvement occurs within 4 weeks, restart RMC-4630 at the same dose level. If the AE re-occurs, consider dose reduction to one dose level lower for RMC-4630 after the AE resolves to Grade 1 or within normal limits or returns to baseline. If the AE does not improve within 4 weeks, consider discontinuation of RMC-4630.
 
Grade 4 pancytopenia: Hold RMC-4630 and sotorasib until resolves to Grade 1, within normal limits or returns to baseline. If improvement occurs within 4 weeks, restart RMC 4630 and sotorasib one dose level lower. If there is no improvement within 4 weeks, discontinue both drugs.

Table 6: Dose Modification Guidelines for RMC-4630 and Sotorasib (Continued)

AE	Action
Rash	
Grade 1-2 (tolerable): Administer supportive care and continue study treatment.
 
Grade 3 or 4: Hold both components of study treatment until improvement to \leq Grade 2.
 
If there is improvement to \leq Grade 2 within 3 weeks, then reduce RMC-4630 by 1 dose level. If recurs, a second dose reduction for RMC-4630 and/or a dose reduction for sotorasib may be considered. If rash continues to occur with 2 dose reductions of RMC-4630 and/or 1 dose reduction of sotorasib, consider permanent discontinuation of RMC-4630. If Grade 3-4 rash does not improve within 3 weeks, permanently discontinue RMC-4630.
 
Stevens Johnson Syndrome (SJS)/Toxic Epidermal Necrolysis (TEN): Any grade, permanently discontinue both components of study treatment

Ocular symptoms	
For neurosensory retinal detachment and other ocular events:
 
Grade 3 or 4 – Hold RMC-4630 until the AE recovers to normal or Grade 1 and re-start RMC-4630 at one dose level lower. For recurrence of a Grade 3 AE, dose interrupt until the AE recovers to normal or Grade 1 and consider a second dose reduction for RMC-4630. Permanently discontinue RMC-4630 if the Grade 3 AE re-occurs after two dose reductions of RMC-4630. For recurrence of a Grade 4 AE, permanently discontinue RMC-4630. Discontinue RMC-4630 for any grade AE of retinal vein occlusion (RVO).

Hemorrhage	
Rule out other causes.
 
Grade 1-2: Continue both components of study treatment at the current doses and monitor closely for signs or symptoms of clinically significant bleeding.
 
Grade 3: Hold RMC-4630 until resolution. If the event resolves within 3 weeks, consider restarting RMC-4630 at a lower dose. If not resolved within 3 weeks, permanently discontinue RMC-4630.
 
Grade 4 or CNS hemorrhage: If hemorrhage is associated with thrombocytopenia or reduced platelet count from baseline, permanently discontinue RMC-4630. If not, hold RMC-4630 until resolution, and restart at a lower dose if resolves within 3 weeks. If not resolved within 3 weeks, permanently discontinue RMC-4630.

Diarrhea/ Nausea/ Vomiting	
Grade 1-2: Maximal supportive care. Continue both components of study treatment at current doses and ongoing prophylaxis maybe considered upon investigator's discretion after the first event
 
Grade 3: Hold both components of study treatment (if receiving maximal supportive care) until the event recovers to Grade 1 or normal or returns to baseline. If improves within 3 weeks, then restart RMC-4630 and sotorasib at 1 dose level lower. If not resolved within 3 weeks, permanently discontinue RMC-4630. If event recurs, hold both components of study treatment and consider a second dose reduction for both components of study treatment or permanent discontinuation of one or both components of study treatment depending on the clinical benefit. Note: Only one dose reduction is applicable for subjects starting dosing at 240 mg of sotorasib.
 
Grade 4: Permanently discontinue RMC-4630 and sotorasib for Grade 4 diarrhea or vomiting

Table 6: Dose Modification Guidelines for RMC-4630 and Sotorasib (Continued)

AE	Action
Liver function tests (AST, ALT, and/or total bilirubin)	
Grade 1: Continue both components of study treatment at current doses.
 
Grade 2 AST or ALT with symptoms OR Grade 3 to 4 AST or ALT elevation: Rule out other causes such as metastatic liver disease, concomitant drugs, infection, hepatitis etc. Hold both RMC-4630 and sotorasib until the event recovers to Grade 1 or within normal limits or returns to baseline, then dose reduce RMC-4630 and sotorasib to one dose level lower. If AE does not improve or recurs, dose reduce another dose level. No dose modification is required for isolated elevations of GGT. Note: Only one dose reduction is applicable for subjects starting dosing at 240 mg of sotorasib.
 
Both components of study treatment should be permanently discontinued for concurrent elevation of AST or ALT $>3 \times$ ULN AND total bilirubin $>2 \times$ ULN or INR >1.5 in the absence of cholestasis and other causes (eg, viral hepatitis, other pre-existing or acute liver disease, or another drug capable of the observed injury), which may indicate severe DILI (potential Hy's law case). If liver injury is due to other causes such as viral hepatitis, acute liver disease, or another drug capable of liver injury, evaluate the extent of liver injury (eg, albumin level, PTT, INR, etc) and if considered to be severe, either consider continuing at a lower dose for both components of study treatment or discontinue one or both components of study treatment.

Hypertension	
Grade 2: Treat according to institutional/provider guidelines in accordance with goal of reduction to Grade 1 or baseline. Continue RMC-4630 and sotorasib.
 
Grade 3: Treat according to institutional guidelines with the goal of reducing blood pressure to Grade 1 or within normal limits or baseline. Consider holding RMC-4630. If there is improvement, restart RMC-4630 at the same dose level or one dose level lower per investigator judgement.
 
Grade 4: Treat according to institutional guidelines. Permanently discontinue RMC-4630.

ILD / pneumonitis	
Any Grade
 
Withhold RMC-4630 and sotorasib if ILD/pneumonitis is suspected.
 
If diagnosis is confirmed, permanently discontinue sotorasib and RMC-4630.

Abbreviations: AE = adverse event; ANC = absolute neutrophil count; ALT = alanine aminotransferase; AST = aspartate aminotransferase; DILI = drug-induced liver injury; GGT = gamma-glutamyl transferase; ILD = interstitial lung disease; INR = international normalized ratio; PTT = partial thromboplastin time; SJS = Stevens-Johnson syndrome; TEN = toxic epidermal necrolysis; ULN = upper limit of normal.

Table 7: General Dose Modification Guidelines with RMC-4630 and Sotorasib for All Other AEs

Severity Grade	Action
Grade 1	Continue both components of study treatment at the current dose
Grade 2	
May continue both components of study treatment without dose interruption and manage the toxicity using institutional guidelines.
 
Dose interruption may be considered for one component of study treatment if the toxicity is a suspected toxicity of RMC-4630 and/or sotorasib, respectively.
 
Upon recovery to baseline or Grade 1, treatment may be restarted at the same dose.
 
If the toxicity re-occurs, consider a dose reduction for one of the components of study treatment if a causal relationship to the AE is suspected with RMC-4630 and/or sotorasib, respectively.

Grade 3	
Hold treatment with both components of study treatment until recovery to normal or baseline or Grade 1 and manage per institutional guidelines.
 
Upon recovery, subject may start RMC-4630 and sotorasib at one dose level lower. If AE re-occurs after one dose reduction, consider a second dose reduction for one or both components of study treatment. Note: Only one dose reduction is applicable for subjects starting dosing at 240 mg of sotorasib.
 
If permanent discontinuation of either component of study treatment is being considered in the setting of re-occurrence of the AEs, RMC-4630 should be discontinued prior to sotorasib.

Grade 4	
Hold treatment with both components of study treatment until recovery to normal or baseline or Grade 1 and manage per institutional guidelines.
 
Upon recovery, a causal relationship should be carefully evaluated with RMC-4630 and permanent discontinuation of RMC-4630 considered for certain Grade 4 AEs. If it decided to continue treatment with RMC-4630, it should be at a reduced dose level.
 
Sotorasib may be continued at one dose level lower upon recovery.
 
If event re-occurs after sotorasib dose reduction and RMC-4630 reduction/discontinuation, consider permanent discontinuation of sotorasib.

Abbreviations: AE = adverse event.

